### 4.1.2. Oral Mucositis is an Unmet Medical Need

Oral mucositis prevention and management remains a substantial unmet need. For years, there has been no substantial change in its management (Keefe 2006). Current guidelines (Lalla, Bowen et al. 2014) from the Multinational Association of Supportive Care in Cancer and the International Society of Oral Oncology (MASCC/ISOO) limit recommended or suggested interventions to prevent OM to:

Kepivance® (palifermin) in the setting of high-dose chemotherapy and total body irradiation, followed by autologous hematopoietic stem cell transplantation (HSCT), for a hematological malignancy. However, Kepivance® is not licensed/approved for the treatment of OM associated with HNC;

Oral cryotherapy in the setting of 5-fluorouracil therapy or chemotherapy/HSCT;

Low-level laser therapy in the setting of chemotherapy/HSCT or chemoradiotherapy for HNC;

Benzydamine mouthwash in the setting of HNC treated with moderate-dose RT, without concomitant chemotherapy;

Oral zinc supplements in the setting of radiation or chemoradiation;

Oral care protocols across all cancer treatment modalities.

Narcotics and doxepin mouthwash are recommended or suggested by MASCC/ISOO for the treatment of OM-related pain. Several other agents currently used to treat OM symptoms, while designed to palliate associated pain or manage infection, do not alter the underlying biologic processes that give rise to OM. MASCC/ISOO currently recommends or suggests *against* the use of some agents that have historically been used (e.g., antimicrobial mouthwashes, sucralfate, chlorhexidine mouthwash), citing evidence for lack of effectiveness against OM in one or more treatment settings.

Galera Therapeutics, Inc.

Version: Amendment 4

Further, no approved product is available in the US (or elsewhere) for OM in the vast majority of these patients, especially those with solid tumors such as SCCHN. At present, palifermin is the only FDA-approved (licensed) product for OM but its indicated use (patients receiving HSCT for hematologic malignancies) is limited to a very small cohort (4%) of the total population at risk for OM: a cohort associated with conditioning regimens prior to stem cell transplant for the treatment of hematologic malignancies. The approval specifically excludes patients with solid tumors (Spielberger, Stiff et al. 2004).

A few medical devices are on the market, but they generally lack sufficient data to allow recommendation. The mucoadhesive MuGard™ is indicated as a palliative treatment for the management of OM but requires administration 4 to 6 times per day for optimal effect and does not alter the mechanism of OM (MuGard prescribing information). The oral gel Gelclair® has a similar use and effect for OM or oral irritation due to other causes but does not affect the mechanism of OM. Caphosol® (supersaturated calcium phosphate rinse) is indicated for xerostomia or as an adjunct to standard oral care for OM but failed to reduce the incidence of ulcerative or severe OM in a recently-published Phase 2 study (Rao, Trotti et al. 2014). The lipid-based oral barrier rinse Episil® and the bacteriostatic rinse GelX® (zinc gluconate-taurine complex) may be used for pain related to OM but do not affect the mechanism causing OM.

Therefore, current standard of care for patients with solid tumors consists of oral care protocols and palliative approaches to deal with painful symptoms. An urgent need remains for novel products, like GC4419, aimed at reducing the incidence and severity of severe OM.

#### **4.2. GC4419 Overview**

GC4419 is a novel, highly stable manganese-containing macrocyclic ligand complex with a molecular weight of 483 g/mol, whose activity mimics that of naturally occurring superoxide dismutase (SOD) enzymes. It is therefore a prototype of a new class of drugs termed selective SOD mimetics. GC4419 selectively removes superoxide anions without reacting with other reactive oxygen species, including nitric oxide, hydrogen peroxide, and peroxynitrite. In addition, unlike native SOD, GC4419 is not deactivated by nitration.

GC4419 is being developed for the initial indication of reduction of the incidence and severity of severe OM induced by RT, with or without systemic therapy, under IND 111,539 with the Division of Dermatology and Dental Products (DDDP), United States FDA.

By efficiently and rapidly removing O2•-, GC4419 offers a treatment paradigm for preventing or controlling OM. Numerous published studies indicate that OM, esophagitis, pneumonitis, fibrosis, or other normal-tissue radiation damage may be reduced by treatment with liposomally encapsulated exogenous manganese (Mn) SOD or a MnSOD transgene, exogenous Cu/Zn SOD, or a dismutase mimetic enantiomerically related to GC4419 (Delanian, Baillet et al. 1994; Epperly, Defilippi et al. 2000; Guo, Seixas-Silva et al. 2003; Murphy, Fey et al. 2008; Thompson, Chu et al. 2010).

GC4419 was studied extensively in nonclinical settings, in different animal models, and various human xenograft and murine syngeneic tumor models (for details see the Investigator's Brochure). Nonclinical data have identified GC4419 as a promising new radioprotective, anticancer and anti-inflammatory agent. GC4419 was active as a radio-protectant in animal models of cancer radiation therapy and added to the activity of chemotherapeutic agents in animal models of cancer. Importantly, GC4419 did not interfere with the anti-tumor effects of either radiation therapy or chemotherapy in animal models of cancer.

Galera Therapeutics, Inc.

Version: Amendment 4

GC4419 was studied in a Phase 1b/2a clinical study, GT-001 (NCT01921426, Anderson, Sonis, et al. 2018) and Phase 2b study, GT-201 (NCT02508389). In study GT-001, GC4419 was administered throughout the full 6- to 7-week course of chemo-radiotherapy (CRT) at doses of either 30 or 90 mg, Monday-Friday (M-F), and appeared to substantially reduce the duration, incidence, and overall severity (defined here as the incidence specifically of Grade 4) of severe OM compared with historical expectations (data are based on 43 evaluable subjects). Further, GC4419 did not appear to increase the known toxicity of the CRT regimen (IMRT plus concurrent cisplatin), nor did it appear to interfere with tumor response to CRT assessed through 1 year post therapy (for details see Anderson, Sonis, et al. 2018 and the Investigator's Brochure). These results supported the design of the randomized, double-blind, placebo-controlled, Phase 2b study GT-201, with two GC4419 doses of 30 and 90 mg selected for comparison with placebo and administered 5 days/week. As in GT-001, patients eligible for GT-201 were required to have locally advanced squamous cell carcinoma of the oral cavity (OC) or oropharynx (OP), with their standard care calling for concurrent IMRT and cisplatin. Results from 223 randomized subjects indicated that GC4419 at daily dose of 90 mg resulted in statistically significant reduction on the primary endpoint, severe OM duration, for subjects on the 90 mg arm compared to placebo, as determined by the non-parametric Van Elteren test. The median duration of SOM, as defined in the protocol, was 1.5 days for subjects receiving 90 mg of GC4419 vs 19 days for subjects receiving placebo (p=0.024). Also, the incidence of SOM during the IMRT treatment period was 43% for subjects receiving 90 mg of GC4419 vs 65% for subjects receiving placebo (nominal p value=0.009), a relative reduction of approximately 34%. The safety profile of GC4419 in combination with the IMRT/platinum regimen in GT-201 study was acceptable; safety results with both the 90 mg dose and the 30 mg dose were similar to those with placebo.

Additional details about the pathogenesis of OM, the mechanism of action of GC4419, and the results of non-clinical testing as well as the clinical trials GT-001 and GT-201 are provided in the Investigator's Brochure.

#### 4.3. Study Period Definitions

**Study Treatment Period:** the period of time from Study Day 1 (IMRT Day 1/Baseline) through the last day of IMRT. Subjects who receive at least 60 Gy of IMRT will be considered to have completed the Study Treatment Period.

**OM** (**Oral Mucositis**) **Observation Period:** the period of time from Study Day 1 (IMRT Day 1/Baseline) through the last OM assessment. By protocol, the last OM assessment is to occur during the second week after completion of IMRT.

**AE** (Adverse Event) Observation Period: the period of time from the date of randomization through 30 days post last day of cisplatin, IMRT, or GC4419/Placebo (i.e., whichever occurs last).

**LTFU** (**Long-term Follow-up**) **Observation Period:** the period of time from last day of IMRT through 24 months post-IMRT.

Galera Therapeutics, Inc.

Version: Amendment 4

# 5. STUDY OBJECTIVES, ENDPOINTS AND PURPOSE

## 5.1. Objectives

# **Primary Objective:**

To assess the effect of GC4419 administered intravenously (IV) on the incidence of severe oral mucositis (SOM; Grade 3-4 OM) during the Study Treatment Period in subjects receiving post-operative or definitive therapy with single-agent cisplatin plus Intensity-Modulated Radiation Therapy (IMRT) for locally advanced, non-metastatic squamous cell carcinoma (SCC) of the oral cavity or oropharynx

## **Secondary Objectives:**

- To assess the effect of GC4419 administered intravenously (IV) on the incidence of Grade 4 OM during the Study Treatment Period in subjects receiving post-operative or definitive therapy with single-agent cisplatin plus Intensity-Modulated Radiation Therapy (IMRT) for locally advanced, non-metastatic squamous cell carcinoma (SCC) of the oral cavity or oropharynx
- To assess the effect of GC4419 administered intravenously (IV) on the total number of days of Grade 3-4 OM during the OM Observation Period in subjects receiving post-operative or definitive therapy with single-agent cisplatin plus Intensity-Modulated Radiation Therapy (IMRT) for locally advanced, non-metastatic squamous cell carcinoma (SCC) of the oral cavity or oropharynx
- To assess the effect of GC4419 administered intravenously (IV) on the total number of days of Grade 4 OM during the OM Observation Period in subjects receiving post-operative or definitive therapy with single-agent cisplatin plus Intensity-Modulated Radiation Therapy (IMRT) for locally advanced, non-metastatic squamous cell carcinoma (SCC) of the oral cavity or oropharynx
- To confirm safety and tolerability of GC4419 administered IV in subjects receiving cisplatin plus IMRT for locally advanced, non-metastatic SCC of the oral cavity or oropharynx

To evaluate potential effects of GC4419 on tumor efficacy outcomes for the study population

## **Exploratory Objectives:**

- To assess duration (per subject) of SOM (WHO Grade 3-4) for subjects who have experienced SOM during the OM Observation Period
- To assess duration of Grade 4 OM for subjects who have experienced Grade 4 OM during the OM Observation Period
- To assess effects of GC4419 on the cumulative incidence of SOM (WHO Grade 3-4) from the first IMRT fraction through the delivery of progressive, cumulative IMRT doses
- To assess effects of GC4419 on the cumulative incidence of SOM (WHO Grade 3-4) during the OM Observation Period
- To assess time from beginning of IMRT and IMRT dose to onset of SOM (WHO Grade 3-4)

To assess resolution (defined as ≤ Grade 2 OM) of SOM (WHO Grade 3-4) before the end of the Study Treatment Period for subjects who have experienced SOM during the Study Treatment Period

Galera Therapeutics, Inc.

Version: Amendment 4

- To assess resolution (defined as ≤ Grade 3 OM) of Grade 4 OM before the end of the Study Treatment Period for subjects who have experienced Grade 4 OM during the Study Treatment Period
- To assess effects of GC4419 on the incidence, onset, and duration of ulcerative OM (≥ Grade 2)
- To assess treatment delivery and delays (number and duration of delays) of IMRT and cisplatin

To assess the relationship between drug exposure and safety/efficacy

To assess the effects of GC4419 on circulating cytokine levels and gene expression levels

To assess the effects of GC4419 on kidney function throughout the first year post-IMRT

## 5.2. Endpoints

### **Primary Endpoint:**

Cumulative incidence of SOM, defined as the proportion of subjects with any occurrence of WHO Grade 3-4 OM, during the Study Treatment Period

## **Secondary Endpoints:**

## **Efficacy:**

- Cumulative incidence of WHO Grade 4 OM, defined as the proportion of subjects with any occurrence of WHO Grade 4 OM, during the Study Treatment Period
- Total number of days (per subject) of SOM (WHO Grade 3-4) during the OM Observation Period for all subjects
- Total number of days (per subject) of Grade 4 OM during the OM Observation Period for all subjects

#### Safety:

Safety of GC4419 as measured by:

- Frequency, duration, and severity of Adverse Events (AEs) and serious AEs
   (SAEs) during the AE Observation Period;
- Incidence and shifts of clinically significant laboratory abnormalities

Effect of treatment on tumor outcomes (locoregional failure, distant metastases, progression-free survival, overall survival) during the LTFU Observation Period

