# 6.2.3. Rationale for Tumor Follow-up and Analysis

Although the mechanism of action, existing nonclinical data (in vitro and in vivo), and existing clinical data with GC4419 uniformly indicate otherwise, there is a theoretical potential for GC4419 to protect the tumor from the therapeutic effects of concurrent chemoradiation. Patient candidates for GTI-4419-301 will be informed of this potential risk and the existing data as part of the consent process and document. GT-001 showed no evidence of tumor protection (See Investigator's Brochure). Tumor follow-up is ongoing for GT-201.

Fakhry et al. published an analysis comparing time to and patterns of progression for HPV-positive and HPV-negative patients treated in RTOG 0129 or RTOG 0522. The rate of progression was similar in the two groups. After a median follow-up of four years, the majority of progression events was found to have occurred in the first year after protocol therapy (Fakhry et al. 2014). This information suggests that tumor control data at one year after protocol treatment may provide a strong indication that results are consistent with expectations. As such, subjects in this Phase 3 trial will be followed for tumor progression for one year after completing treatment. Subjects will continue follow-up past that point for overall survival only.

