Weekly	X					X					X					X				
Radiation 	X	X	X	X	X	X	X	X	X	X	X	X	X	X	X	X	X	X	X	X

Galera Therapeutics, Inc.

Treatment	Week 5				Week 6					Week 7					
	Day	Day	Day	Day	Day	Day	Day	Day	Day	Day	Day	Day	Day	Day	Day
	29	30	31	32	33	36	37	38	39	40	43	44	45	46	47
GC4419/Placebo 	X	X	X	X	X	X	X	X	X	X	X	X	X	X	X
Cisplatin  Tri-Weekly											X				
Weekly	X					X					$X^4$				
Radiation 	X	X	X	X	X	X	X	X	X	X	X	X	X	X	X

¹ Intravenous GC4419/Placebo is administered by a 60-minute intravenous infusion (±6 min) once a day for the first 35 days of IMRT (Monday through Friday). IMRT must be initiated as soon as possible upon completion of GC4419/Placebo infusion, but no later than 60 minutes post GC4419/Placebo infusion. On Day 1/Baseline, chemotherapy prehydration and infusion should be administered after GC4419/Placebo infusion and IMRT, if possible. If IMRT is not received on any given day due to a treatment break or unforeseen circumstances, GC4419/Placebo should not be administered on that day. Subjects should resume GC4419/Placebo administration when IMRT resumes. If a subject is scheduled to receive IMRT on a weekend day (e.g., to make-up for a holiday site closure), the Investigator should contact the Medical Monitor for a discussion prior to IMRT administration.

<sup>2 Cisplatin monotherapy should be administered in a standard q3 weeks regimen (100 mg/m^2) or weekly regimen (40 mg/m^2). Anti-emetic prophylaxis and hematopoietic growth factor use should be administered per ASCO guidelines. If institutional guidelines permit, cisplatin may be administered prior to or after the first day of IMRT. On days in which chemotherapy and GC4419/Placebo are administered, the administration sequence should be GC4419/Placebo, IMRT, prehydration, and then cisplatin, if possible. Patients treated with induction chemotherapy prior to concomitant chemoradiation are not eligible for this study.

Clinical Study Protocol GTI-4419-301 Confidential

 Eligible patients will be scheduled to receive a continuous course IMRT delivered in single daily fractions of 2.0 to 2.2 Gy, five days per week (Monday through Friday), with a cumulative radiation dose of 60-72 Gy. Planned radiation treatment fields must include at least two oral sites (buccal mucosa, floor of mouth, tongue, soft palate) that are each planned to receive  $\geq$  50 cumulative Gy.

Galera Therapeutics, Inc.

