#### 10.6. Tumor Status Assessment

## **10.6.1.** Clinical Tumor Assessment

The subject's tumor status will be assessed clinically at the following time points:

Last day of IMRT

Every 3 months,  $\pm$  30 days, throughout the 1st year post-IMRT (Months 3, 6, 9, and 12)

The following tumor status information will be collected at each of the above time points:

Disease progression – locoregional and distant metastasis

Development of second primary tumors

Additional malignancies

A head/neck/oral exam to assess the tumor status is sufficient on the Last day of IMRT if disease progression is not suspected. If disease progression is suspected, a laryngopharyngoscopy should be conducted on the Last day of IMRT.

At Months 3, 6, 9, and 12 post-IMRT, a brief history & a physical examination by a Radiation Oncologist, Medical Oncologist, ENT, or Head & Neck Surgeon, including a laryngopharyngoscopy (mirror and/or fiberoptic and/or direct procedure), must be conducted. If local/regional progression or recurrence has already been discovered at a previous visit, a laryngopharyngoscopy is no longer required at future visits. However, if distant progression is

discovered at a previous visit, a laryngopharyngoscopy is still required at subsequent visits to assess the subject for local/regional progression/recurrence. A head/neck/oral exam must always be conducted at months 3, 6, 9, and 12 post-IMRT.

Galera Therapeutics, Inc.

Version: Amendment 4

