# **10.6.2.2.** Post-Treatment Tumor Imaging

Radiographic imaging must be performed at Month 12 post-IMRT for all subjects. Subjects treated definitively (as opposed to post-operatively) will also undergo imaging at Month 3 post-IMRT to assess tumor response/clearance to the degree possible.

Radiographic imaging is highly recommended at any post-IMRT follow-up visit at which disease progression is suspected by the treating physician. If radiographic imaging is performed, both local/regional recurrence and distant metastases should be evaluated.

When possible, the same imaging technique (i.e., CAT, PET, or MRI) that was used for pretreatment tumor imaging at the time of staging should be used for post-treatment tumor imaging.

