#### 10.6.3. Survival Status

Subjects will be followed for survival for two years after IMRT:

Every 3 months,  $\pm$  30 days, throughout the 1st year post-IMRT (Months 3, 6, 9, and 12)

Every 4 months,  $\pm$  30 days, throughout the 2nd year post-IMRT (Months 16, 20, and 24)

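### Locoregional failure, distant metastases and PFS are defined over 24 months post-IMRT, but tumor assessment is scheduled only to Month 12

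*Combined protocol and SAP*

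**What the plan says.** The synopsis and Section 5.2 (Secondary Endpoints, Safety) give one window to four tumor outcomes: "Effect of treatment on tumor outcomes (locoregional failure, distant metastases, progression-free survival, overall survival) during the LTFU Observation Period". Section 4.3 defines that window as "the period of time from last day of IMRT through 24 months post-IMRT".

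The follow-up sections describe two lengths of follow-up.

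- Section 6.2.3: "subjects in this Phase 3 trial will be followed for tumor progression for one year after completing treatment". It then adds: "Subjects will continue follow-up past that point for overall survival only".
- Section 10.6.1, after an assessment on the last day of IMRT: "At Months 3, 6, 9, and 12 post-IMRT, a brief history & a physical examination", each with a ±30-day window.
- Section 10.6.2.2: "Radiographic imaging must be performed at Month 12 post-IMRT for all subjects". Definitively treated subjects are also imaged at Month 3.
- Section 10.6.3: "Subjects will be followed for survival for two years after IMRT", with year-2 contacts at Months 16, 20 and 24.
- Section 10.10.2 and Table 6 agree: in year 2 the only item is survival status.

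For analysis, Section 12.8.2 plans tabulated frequencies of locoregional and distant failure. It also plans ordinary Kaplan-Meier cumulative event curves for OS, PFS, locoregional failure and distant metastases. Section 12.1 refers technical detail to a separate SAP, which governs in a conflict. The text of that SAP was not among the material supplied for this review.

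**The concern.** Read literally, three of the four outcomes cover a second year in which nobody is scheduled to look for the event. PFS is the most exposed. After the Month 12 visit its death component is still collected and its progression component is not, so a PFS curve drawn over the stated window silently changes definition halfway.

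This matters because Section 6.2.3 says tumor follow-up is there to address a theoretical risk that GC4419 protects the tumor from chemoradiation. If later progression goes unrecorded, both arms look better than they are and a year-2 difference between arms cannot show itself.

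A smaller question concerns method. Death without locoregional failure, or without metastasis, competes with that failure. If such deaths are censored, one minus Kaplan-Meier overstates the proportion of subjects who actually fail.

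**Working it through.** The protocol gives no event rate, precision or power for any tumor outcome, so there is no stated figure to reproduce. Step 1 uses protocol inputs only. Steps 2 and 3 use assumed rates, shown as ranges.

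**Step 1: window against schedule**

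| Outcome | Stated window (5.2 with 4.3) | Last scheduled assessment |
|---|---|---|
| Locoregional failure | to Month 24 | Month 12 (10.6.1, 10.6.2.2, Table 6) |
| Distant metastases | to Month 24 | Month 12 (10.6.1, 10.6.2.2, Table 6) |
| PFS | to Month 24 | progression Month 12; death Month 24 |
| OS | to Month 24 | Month 24 (10.6.3) |

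The latest Month 12 visit falls 365 + 30 = 395 days after IMRT, and 395/30.44 = 12.98 months. The uncovered time is 24 − 12.98 = 11.0 months, and 11.0/24 = 46%.

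**Step 2: PFS if subjects stay at risk to Month 24 and only deaths count in year 2**

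Assumptions: 12-month progression p = 15-25%, 12-month death d = 5-10%, and a year-2 progression hazard equal to r times the year-1 hazard. Section 6.2.3 cites an analysis in which most progression fell in the first year, so r = 1 is an upper bound.

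- Apparent 24-month PFS = (1−p)(1−d)²
- True 24-month PFS = (1−p)^(1+r) × (1−d)²

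With p = 0.15, d = 0.05, r = 0.25: apparent 0.85 × 0.9025 = 76.7%; true 0.85^1.25 × 0.9025 = 73.7%; excess 3.1 points before rounding.

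| p / d | Apparent | True (excess), r = 0.25 | r = 0.5 | r = 1 |
|---|---|---|---|---|
| 15% / 5% | 76.7 | 73.7 (3.1) | 70.7 (6.0) | 65.2 (11.5) |
| 15% / 10% | 68.8 | 66.1 (2.7) | 63.5 (5.4) | 58.5 (10.3) |
| 25% / 5% | 67.7 | 63.0 (4.7) | 58.6 (9.1) | 50.8 (16.9) |
| 25% / 10% | 60.8 | 56.5 (4.2) | 52.6 (8.1) | 45.6 (15.2) |

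The model keeps the death rate unchanged after an unrecorded progression. If progression raises mortality before Month 24, some of the loss is recovered as deaths and the excess is smaller.

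For locoregional failure or metastases, with 12-month net failure of 10-25%, the share of 24-month events falling in year 2 is (T − p)/T, where T = 1 − (1−p)^(1+r). That is 17-19% at r = 0.25 and 43-47% at r = 1.

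**Step 3: Kaplan-Meier against cumulative incidence at Month 12**

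Constant cause-specific hazards, a = −ln(1 − net failure) and b = −ln(1 − death):

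incidence = a/(a+b) × (1 − exp(−(a+b)))

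| Net failure / death | 1 − Kaplan-Meier | Cumulative incidence | Overstatement |
|---|---|---|---|
| 8% / 3% | 8.00 | 7.88 | 0.12 |
| 15% / 6% | 15.00 | 14.56 | 0.44 |
| 20% / 12% | 20.00 | 18.82 | 1.18 |

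Effect on the difference between arms:

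| Net failure | Death | Kaplan-Meier | Cumulative incidence |
|---|---|---|---|
| 8 vs 12% | 3% both | 4.00 | 3.94 |
| 14 vs 20% | 12% both | 6.00 | 5.66 |
| 14 vs 20% | 6 vs 12% | 6.00 | 5.23 |
| 15 vs 15% | 4 vs 8% | 0.00 | −0.30 |

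For comparison, the 95% CI half-width of an arm difference with the planned 240 and 160 ITT subjects is 1.96 × √(p(1−p)(1/240 + 1/160)): 5.4 points at p = 8% and 8.0 points at p = 20%.

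**The case against.** The best defence is that the operational text is clear. Section 6.2.3 chooses one year of tumor follow-up on purpose and gives a reason, and Section 10.10.2 repeats it. No section plans a 24-month figure for locoregional failure, metastases or PFS, and censoring at the last tumor assessment would remove the consequence in Step 2. Such a rule may be in the SAP. This stands to the extent that the bias is conditional and the schedule is not at fault. It does not remove the contradiction between Sections 4.3 and 5.2 and the follow-up sections. The Amendment 4 summary says the study period definitions were added to align the protocol with the final SAP, so there is no ground for assuming that the SAP uses a 12-month window. The synopsis places tumor results after the last subject completes long-term follow-up. OS alone would explain that timing, so it settles nothing.

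Imaging on suspicion of progression does not fill the gap. It is recommended rather than required, and Section 10.10.2 ties it to the Month 3-12 visits.

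On method, the objection is largely right. The overstatement arises only if deaths are censored, which the protocol does not state. It is small at Month 12, and crude frequencies are planned alongside. Cumulative incidence also answers a different question. In the 15 vs 15% example it shows a failure difference produced by deaths alone, whereas the death-censored curve tracks failure among those still at risk, provided censoring is independent. The choice is one of estimand.

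**Conclusion.** The window contradiction holds for locoregional failure, distant metastases and PFS, and not for OS. The 46% gap rests on protocol figures alone. The PFS excess of 2.7-9.1 points (r = 0.25 to 0.5) rests on assumed rates and on subjects being kept at risk to Month 24. The Kaplan-Meier matter is an improvement worth making: 0.1-1.2 points in one arm and up to 0.8 in the arm difference, also on assumed rates.

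Three stronger readings are tempting and unsupported.

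- A reader might infer that year-2 tumor visits were forgotten. Section 6.2.3 shows that they were left out deliberately.
- A reader might infer that the missing time origin and censoring rule are errors. Section 12.1 leaves such detail to the SAP.
- A reader might infer that the estimate needs a new origin at Day 1 and a fixed day beyond the visit window. The protocol plans no such reading and schedules its tumor visits from the end of IMRT. Nominal visits serve without crediting unexamined days as event-free.

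Severity is minor. These outcomes are descriptive and lie outside the multiplicity procedure, and the primary and key secondary efficacy results do not depend on them.

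**What to change.** In the synopsis and Sections 5.2 and 12.8:

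1. Evaluate locoregional failure, distant metastases and PFS through the Month 12 post-IMRT assessment. Analyse assessments at their nominal visits (Months 3, 6, 9 and 12), and for these three outcomes censor event-free subjects at their last tumor assessment.
2. Evaluate OS through Month 24.
3. As a cheap improvement in Section 12.8.2, report cumulative incidence for locoregional failure and distant metastases, with death without that failure as a competing event. Keep Kaplan-Meier for OS and PFS. Death-censored curves for the two failure types may stay as a supplement. Check first whether the SAP already provides this.

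The cost is endpoint and analysis wording plus minor programming, with no new visits or data. The downside is that no 24-month estimate of locoregional failure, metastases or PFS is reported, which the schedule cannot support in any case. The changes should be settled before the unblinded tumor analysis.
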